### **Performance Status**

ECOG performance status will be summarized at baseline and each post-baseline scheduled visit. Summaries will use frequency and percentage of subjects at each planned assessment time. A summary of change from baseline by scheduled visits will be performed, as well as the worst case post-baseline and the best case post-baseline changes during the study (improved, no change, deteriorated).

A supporting listing will also be provided.

### **ECG**

A summary of the number and percentage of subjects who had normal and abnormal (clinically significant and not clinically significant) ECG findings at screening/baseline will be provided.

### **Organ Examination**

The number and percentage of subjects with normal or enlarged organs based on liver and spleen examination by palpation/CT scan will be summarized by scheduled visits.

A supporting listing will also be provided.

## **13. HEALTH OUTCOMES ANALYSES**

All analyses described in this section will be performed using the ITT population. Data from all questionnaires, including translated versions, will be pooled for analysis.

The EORTC QLQ-C30, EORTC QLQ-CLL16, and EQ-5D should be administered at baseline and at treatment clinic visits; Days 1 and 85, and follow-up visits post treatment; every 3 months through Month 60. The Health Change Questionnaire should be administered at all the aforementioned post-baseline visits. If a subject demonstrates disease progression, the measures should be completed at the progression visit and again one time after determination of progression. If a subject in PD will be available and willing, post-PD questionnaires may be administered through the date that would correspond to the subject's Month 60 visit. If a subject withdraws from the study then the PRO questionnaires should be administered at the point of withdrawal.

### **13.1. Patient Reported Constitutional Symptoms ('B-Symptoms') Score**

#### **Background:**

The EORTC QLQ-C30 and QLQ-CLL16 module include items asking about symptoms due to CLL and other problems commonly associated with CLL or its treatment, such as

increase risk of infections. To provide a clear indication of the change in constitutional or 'B'-symptoms, [REDACTED], namely, need to rest (C30 item 10), felt weak (C30 item 12), tired (C30 item 18), weight loss (CLL item 31), temperature changes (CLL item 35), night sweats (CLL item 36) lethargic (CLL item 39), slowed down (CLL item 40). This endpoint labeled as 'B-symptoms' score is proposed to provide patient reported data that might be supportive of the 'B-symptoms' clinician rating as well as record improvement in symptoms with each therapy. [REDACTED]

### Calculation of patient reported B-symptoms score

Since the psychometric validation has not been conducted at the time of RAP development, [REDACTED]

### Calculating the 'fatigue' subscore:

There are five items, namely, need to rest (C30 item 10), felt weak (C30 item 12), tired (C30 item 18), lethargic (CLL item 39) and slowed down (CLL item 40) that are reflective of 'extreme fatigue' (one of the four B-symptoms). The fatigue subscore is therefore calculated as follows:

- a. Compute the mean if at least 3 of the 5 items have a score of 3 or more.  $XE = \text{Mean of (Q10, Q12, Q18, Q39, Q40)}$
- b. Carry out a linear transformation to convert to a 0-100 scale:  $TE = (XE - 1) / 3 * 100$
- c. If less than 3 of the items have a valid score treat the scale as missing.

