### Calculating the 'weight loss', 'fever' and 'night sweats' subscores

Since there is only one item reflective for each of the three B-symptoms (weight loss, night sweats and fever), each of these items are treated individually. Therefore, a subscore for each of the three items will be calculated if the subject scored 3 or more for that item. These scores then should be linearly transformed to a 0-100 scale as follows:

- WL: Weight Loss (item 31)  $WL = (Q31 - 1) / 3 * 100$
- TC: Temperature changes (item 35)  $TC = (Q35 - 1) / 3 * 100$
- NS: Night sweats (item 36)  $NS = (Q36 - 1) / 3 * 100$

If a subject does not respond to any one of the 3 items (QLQ-CLL item 31, QLQ-CLL item 35 and QLQ-CLL item 36), the score for that item will be deemed 'missing'.

Depending on the number of subscores reported, the B-symptom score will be calculated as a mean of those sub-scores

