**Summaries and Analyses:**

Changes from baseline scores over time in patient reported B-symptoms score will be analyzed with a repeated measures analysis of covariance (ANCOVA). Analyses will be carried out using PROC MIXED in SAS: baseline score, age group, performance status, and Binet stage, time, treatment, baseline by time, and treatment by time interaction will be fitted as fixed effects, and time will be treated as the repeated variable within subject. Restricted maximum likelihood (REML) will be used to estimate the parameters of the model. An unstructured variance-covariance matrix in the repeated measures model will be used. The model may be modified if required in order to obtain convergence.

Treatment comparisons, including estimated treatment difference, 95% confidence intervals and associated p-values will be provided.

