**Multi-item Scales**

**FA: Fatigue Scale:** Items 39, 40

- a. Compute the mean if at least one item has a valid score. XFA = Mean of (Q39, Q40)
- b. Carry out a linear transformation to convert to a 0-100 scale:  $FA = (XFA - 1) / 3 * 100$

c. If both items do not have a valid score treat the scale as missing.

**TSE: Treatment Side Effects Scale:** Items 31, 32, 35, 37

a. Compute the mean if at least 2 of the items have a valid score.  $XTSE = \text{Mean of (Q31, Q32, Q35, Q37)}$

b. Carry out a linear transformation to convert to a 0-100 scale:  $TSE = (XTSE - 1) / 3 * 100$

c. If less than 2 of the items have a valid score treat the scale as missing.

**DSE: Disease Effects Scale:** Items 33, 34, 36, 38

a. Compute the mean if at least 2 of the items have a valid score.  $XDSE = \text{Mean of (Q33, Q34, Q36, Q38)}$

b. Carry out a linear transformation to convert to a 0-100 scale:  $DSE = (XDSE - 1) / 3 * 100$

c. If less than 2 of the items have a valid score treat the scale as missing.

**IN: Infection Scale:** Items 43, 44, 45, 46

a. Compute the mean if at least 2 of the items have a valid score.  $XIN = \text{Mean of (Q43, Q44, Q45, Q46)}$

b. Carry out a linear transformation to convert to a 0-100 scale:  $IN = (XIN - 1) / 3 * 100$

c. If less than 2 of the items have a valid score treat the scale as missing.

**B. Single-item Scales,** Items 41 and 42

These items are treated individually and should be linearly transformed to a 0-100 scale.

**SP:** Social problems (item 41)  $SP = (Q41 - 1) / 3 * 100$

**FH:** Future health (item 42)  $FH = (Q42 - 1) / 3 * 100$

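### As written, the patient-reported B-symptom score gives no value below a severity threshold of 3, so patients with no or mild symptoms have no score and an added symptom can lower the total

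*SAP*

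**What the plan says.** SAP 13.1 takes eight items, each answered 1 to 4, and forms four subscores.

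- **Fatigue** (items 10, 12, 18, 39, 40), step a: "Compute the mean if at least 3 of the 5 items have a score of 3 or more". All five items then enter the mean, which is rescaled to 0-100. Step c: "If less than 3 of the items have a valid score treat the scale as missing".
- **Weight loss, temperature change, night sweats** (items 31, 35, 36): "a subscore for each of the three items will be calculated if the subject scored 3 or more for that item". A subscore is called missing only for non-response: "If a subject does not respond to any one of the 3 items".
- **Total**: "Depending on the number of subscores reported, the B-symptom score will be calculated as a mean of those sub-scores".

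The background paragraph of 13.1 says the score should support the clinician rating "as well as record improvement in symptoms with each therapy". The analysis is a repeated-measures ANCOVA of change from baseline with baseline score as a covariate: "Treatment comparisons, including estimated treatment difference, 95% confidence intervals and associated p-values will be provided". For the four-item QLQ-CLL16 scales, SAP 13.2 uses the same three-step layout with a different condition: "Compute the mean if at least 2 of the items have a valid score".

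The later SAP for the analysis at 280 PFS events keeps Table 4.0120, the analysis of change in this score, and carries the interim data rules forward.

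**The concern.** Steps a and c of the fatigue rule test different things: severity in one, response in the other. A patient who answers 4, 4, 2, 2, 2 fails step a, so no mean is computed, yet step c does not make the subscore missing. The three single items have the same gap, because an answered 1 or 2 is neither scored nor missing.

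The gap falls where this trial's patients are likely to be. They enter in CR or PR, and CR requires the absence of clinician-rated constitutional symptoms (Protocol 6.2.1.1). Patients' own answers may differ, but few or mild symptoms at baseline would be unsurprising.

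Read literally, a patient without a baseline score has no change score at any visit. A symptom that resolves does not register as improvement. Its subscore disappears, which either removes the total or changes its denominator. Whether a value is missing then depends on the outcome itself, in a comparison that reports confidence intervals and p-values.

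**Working it through.** **Inputs (SAP 13.1).** Items are scored 1-4. The transform is T(x) = (x − 1)/3 × 100, so answers 1, 2, 3 and 4 map to 0, 33.3, 66.7 and 100. The transform alone reproduces the stated 0-100 scale.

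**Two rules compared.**
- *As written*: fatigue is scored only if at least 3 of its 5 items are 3 or more; a single item is scored only if it is 3 or more; the total is the mean of the subscores that exist.
- *Valid-score*: every answered item is scored. With complete answers, the total is the mean of four subscores.

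**Attainable range.** The lowest fatigue subscore as written comes from 3, 3, 3, 1, 1: the mean is 11/5 = 2.2 and T = 40. Each single-item subscore can only be 66.7 or 100. The total therefore runs from 40 to 100, and the stated 0-100 scale is not reproduced.

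**Worked patterns** (fatigue items all 1 unless stated; WL = weight loss, NS = night sweats; unlisted single items are 1).

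| Answers | As written | Valid-score |
|---|---|---|
| All items 1 | no score | 0 |
| All items 2 | no score | 33.3 |
| Fatigue 4,4,2,2,2; single items 2 | no score | (60 + 3 × 33.3)/4 = 40 |
| NS 3 | 66.7 | 16.7 |
| NS 2 | no score | 8.3 |
| NS 4 | 100 | 100/4 = 25 |
| NS 4, WL 3 | (100 + 66.7)/2 = 83.3 | 166.7/4 = 41.7 |
| WL 4, NS 3 | 83.3 | 41.7 |
| WL 4, NS falls to 1 | 100 | 25 |
| NS 4, fatigue 3,3,3,1,1 | (100 + 40)/2 = 70 | (100 + 40)/4 = 35 |

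**Full enumeration.** There are 4^8 = 65,536 complete answer patterns.
- *No score*: 512 of the 1,024 fatigue patterns fall short of the threshold, and each single item falls short in 2 of 4 answers, so 512 × 2³ = 4,096 patterns (6.25%) have no total.
- *Reversals*: raise one item by one point. In 363,648 such steps a score exists before and after, and in 51,081 of them (14.0%) the score falls. The largest fall is 30 points, for example 100 to 70 when night sweats are 4 and fatigue goes from 3,3,2,1,1 to 3,3,3,1,1.
- Under the valid-score rule no worsening lowers the score.

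These counts weight every pattern equally. They describe the rule, not patients.

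**Possible share of assessments without a score.** The documents give no item prevalences, so these are assumptions. Items were simulated from a shared normal latent variable with within-person correlation 0.3 to 0.5, 1,000,000 draws per setting.

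| Assumed share answering 3 or more | Assessments with no score |
|---|---|
| 5% on every item | 87-88% |
| 10% on every item | 75-77% |
| 20% on every item | 54-59% |
| Fatigue items 30-40%, single items 10% | 55-66% |

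**Alternative convention.** If a subscore below the threshold is set to 0 and the total always divides by four, every pattern has a score and none of the 393,216 one-step worsenings lowers it. All items at 2 then scores 0 instead of 33.3.

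**The case against.** The strongest reply is that the scoring rule cannot be fully seen. Two stretches of 13.1 are redacted, including the rest of the sentence that opens the calculation section, and SAP 9.2 refers to separate dataset specifications for full derivations. A convention scoring 0 below the threshold could sit there, and it would remove both the missing scores and the reversals. This stands as a limit on certainty. It fits the visible text poorly, though, because an average over however many subscores are reported implies a varying denominator.

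A threshold of 3 may also be deliberate, since the fatigue items are tied to extreme fatigue and the clinician rating is present or absent. That would justify a presence indicator with absence scored 0. It would not justify leaving absence without a value.

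For fatigue the threshold acts on the scale, not on each item: once three items reach 3, lower answers do count. The no-value problem is exact for the three single items, and for fatigue when the scale condition is not met.

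The stakes are modest. SAP 8.4 makes other secondary p-values nominal, the 280-event SAP calls its results descriptive, and the last SAP's output list has no Health Outcomes section. This limits the consequence but does not repair the rule.

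**Conclusion.** The concern holds for the rule as written. The score has no value when symptoms are absent or mild, cannot go below 40, and can move the wrong way when a symptom appears or resolves. It therefore cannot reliably record improvement, and missingness in the arm comparison depends on the outcome. The direction and size of any bias between arms are not established.

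The pattern results need only the visible text and complete answers. The shares of assessments without a score rest on assumed prevalences and correlations. Confidence is medium because of the redactions. The matching layout in 13.2 and the wording of step c suggest a drafting slip in which a severity condition replaced a valid-response condition. It should be fixed, but the consequence is confined to one supportive, unvalidated patient-reported measure.

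**What to change.** In SAP 13.1:

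- **Fatigue**: compute the mean when at least 3 of the 5 items have a valid response, which brings step a into line with step c.
- **Weight loss, temperature change, night sweats**: subscore = (item − 1)/3 × 100 whenever the item is answered.
- **Total**: mean of the available subscores with a stated minimum, for example 2 of 4. This borrows the half rule that 13.2 applies to items in its four-item scales; another minimum could be justified.
- If 3 or more was meant to mark presence, analyse presence as a separate binary outcome with absence coded 0.
- If a value below the threshold is already defined elsewhere, state it in 13.1.

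The cost is a change of SAP wording and one re-derived variable; all items are already collected. Where results have been produced under the threshold rule, report the re-derived analysis beside them and identify the change in the study report.

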### Calculating the 'weight loss', 'fever' and 'night sweats' subscores

Since there is only one item reflective for each of the three B-symptoms (weight loss, night sweats and fever), each of these items are treated individually. Therefore, a subscore for each of the three items will be calculated if the subject scored 3 or more for that item. These scores then should be linearly transformed to a 0-100 scale as follows:

- WL: Weight Loss (item 31)  $WL = (Q31 - 1) / 3 * 100$
- TC: Temperature changes (item 35)  $TC = (Q35 - 1) / 3 * 100$
- NS: Night sweats (item 36)  $NS = (Q36 - 1) / 3 * 100$

If a subject does not respond to any one of the 3 items (QLQ-CLL item 31, QLQ-CLL item 35 and QLQ-CLL item 36), the score for that item will be deemed 'missing'.

Depending on the number of subscores reported, the B-symptom score will be calculated as a mean of those sub-scores

**Summaries and Analyses:**

Changes from baseline scores over time in patient reported B-symptoms score will be analyzed with a repeated measures analysis of covariance (ANCOVA). Analyses will be carried out using PROC MIXED in SAS: baseline score, age group, performance status, and Binet stage, time, treatment, baseline by time, and treatment by time interaction will be fitted as fixed effects, and time will be treated as the repeated variable within subject. Restricted maximum likelihood (REML) will be used to estimate the parameters of the model. An unstructured variance-covariance matrix in the repeated measures model will be used. The model may be modified if required in order to obtain convergence.

Treatment comparisons, including estimated treatment difference, 95% confidence intervals and associated p-values will be provided.

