**Randomization and Stratification:**

Subjects will be randomized 1:1 to treatment arm A or B.

Eligible subjects will be stratified at randomization based on:

- 1) CR or PR at study entry
- 2) Number of previous induction treatments (2 vs 3)
- 3) Type of prior treatment : chemoimmunotherapy, only alkylating monotherapy, or other treatment

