## 8.2. Other Strata and Covariates

In all efficacy analyses, the tests will be stratified by the baseline stratification factors: (1) CR or PR at study entry, (2) number of previous induction treatments (2 vs 3) and (3) type of prior treatment : chemoimmunotherapy, only alkylating monotherapy, or other treatment. The demographic summaries will document the number of subjects who fall into each stratum for the ITT population. PFS, the primary endpoint, will also be summarized according to the stratification factors.

Subjects will be considered to fall into the respective stratification categories according to the actual data given in the eCRF. Hence, if any misallocations took place in the stratification, it will be the actual data which will be used to determine the stratification of the subject rather than the data as recorded on RAMOS.

In addition to stratification factors, treatment arm as well as age, gender and race will be considered as covariates in the Cox regression model to assess the effect of ofatumumab maintenance treatment vs. no further treatment.

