- Time to progression after next-line therapy

This endpoint will be defined as time (in months) from progression following randomization until progression or death following next-line therapy and counting as events deaths prior to next-line therapy. Analysis of this endpoint will only include subjects who received next-line therapy and who also had PD prior to receiving next-line therapy. Subjects with PD who died prior to receiving next-line therapy will also be included. Subjects who receive next-line therapy with a PD prior to receiving next line therapy and who do not have progression or death after next-line therapy will be censored at their last date of contact. If a subject dies prior to next-line therapy, this will count as an event. [REDACTED]

- Changes in patient reported outcome scores

Area under the curve (AUC) of change from baseline over time in the EORTC QLQ-C30, EORTC QLQ-CLL16 domain scores and total scores as well as the EQ-5D utility and VAS scores will be evaluated. Details of the methods used to evaluate changes in PRO domain and total scores will be provided in the Health Outcomes section of the RAP.

- Improvement of ECOG performance status

Improvement is defined as a decrease from baseline by at least one step on the ECOG performance status scale (improvement categorized as yes or no). The proportion of subjects with improvement will be compared between treatment groups with the Cochran-Mantel-Haenszel test adjusting for stratification factors (response at entry, number of prior treatments and type of prior treatment).

- B-symptoms/Constitutional symptoms

The proportion of subjects with no night sweats, no weight loss, no fever and no extreme fatigue will be summarized and compared to the proportion of subjects with at least one of the following: night sweats, weight loss, fever or extreme fatigue. The proportions will be compared between treatment groups with the Cochran-Mantel-Haenszel test adjusting for stratification factors (response at entry, number of prior treatments and type of prior treatment).

- Incidences of and number of subjects with grade 3 and 4 infections

The number and percentage of subjects with grade 3, 4 and 5 infections will be summarized by treatment group.

- Evaluation of myelosuppression (anemia, neutropenia, thrombocytopenia)

The number and percentage of subjects with myelosuppression will be summarized by treatment group.

- Frequency of transfusions

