**Summaries and Analyses:**

The same analyses for each domain will be conducted as described for patient reported B-symptoms.

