### **13.5. Health Change Questionnaire**

The health Change Questionnaire (HCQ) used is a nine item scale that asks the patient to rate change in status since beginning treatment on this study. Scale choices are :

- A great deal better
- Moderately better
- A little better
- Almost the same, hardly any better
- Unchanged
- Almost the same, hardly any worse
- A little worse
- Moderately worse
- A great deal worse

A summary of the percentage of subjects in each category will be provided.

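### The repeated-measures model for patient-reported scores omits the three randomisation factors; if those factors predict the scores, its standard errors are modestly too large

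*SAP*

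**What the plan says.** - **Randomisation.** SAP Section 3 stratifies by three factors: "CR or PR at study entry"; the number of previous induction treatments, two or three; and "Type of prior treatment : chemoimmunotherapy, only alkylating monotherapy, or other treatment".
- **General rule.** SAP 8.2: "In all efficacy analyses, the tests will be stratified by the baseline stratification factors". SAP 9.2.14 repeats this. Both take the strata from the actual eCRF data, not from the randomisation system. Section 9.2.14 adds that a further stratum may be needed for subjects with one or more than three previous inductions.
- **Where patient-reported outcomes (PROs) sit.** SAP 11.2, Secondary Efficacy Analyses, includes changes in PRO scores and then defers the method: "Details of the methods used to evaluate changes in PRO domain and total scores will be provided in the Health Outcomes section of the RAP".
- **The model.** SAP 13.1 uses restricted maximum likelihood and an unstructured covariance. Its fixed effects are given thus: "baseline score, age group, performance status, and Binet stage, time, treatment, baseline by time, and treatment by time interaction will be fitted". The only stated licence to alter the model is non-convergence. It yields treatment differences, 95% confidence intervals and p-values.
- **Reach.** For QLQ-CLL16, QLQ-C30 and EQ-5D: "The same analyses for each domain will be conducted as described for patient reported B-symptoms". The Health Change Questionnaire is not modelled: "A summary of the percentage of subjects in each category will be provided".
- **Status of the p-values.** SAP 8.4 labels results at or below 0.05 on the other secondary endpoints as nominally significant, without multiplicity control.

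**The concern.** Stratified randomisation forces near-balance on the three factors. If they are prognostic, the true sampling variance of the treatment difference is already reduced. A model that omits them leaves their variance in the residual, so it reports a standard error larger than the design delivers. What is at stake is some precision in the modelled PRO comparisons, and their consistency with neighbouring analyses. Improvement in response, ECOG improvement, clinician-rated constitutional symptoms, autoimmune haemolytic anaemia and minimal residual disease are all compared in SAP 11.2 by Cochran-Mantel-Haenszel tests adjusted for the three factors. Clinician-rated B-symptoms are therefore adjusted for the strata and patient-reported B-symptoms are not. The SAP gives no reason for the difference.

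**Working it through.** **1. Is there a planned figure to reproduce?** Not for PROs: the documents give no standard deviation, target difference, power or interval width. The sample-size figures concern progression-free survival. They reproduce (hazard ratio 28/39.2 = 0.714; Schoenfeld 278 and Freedman 283 events against a stated 280), but they say nothing about PRO precision.

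**2. The texts side by side.** Covariates in 13.1: baseline score, age group, performance status, Binet stage. Factors in 8.2: response at entry, number of inductions, type of prior treatment. The two lists do not overlap. The protocol's PRO section leaves the tests to the analysis plan, so it does not settle the matter.

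**3. Size.** Let R² be the share of residual variance, after the 13.1 covariates, that the three factors explain. R² is an assumption; the documents do not give it.

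- With balanced factors, the true variance of the treatment difference is proportional to 1 − R². The model without the factors reports a variance proportional to 1.
- Ratio of standard errors, omitted to included: 1/√(1 − R²). At R² = 10%, 1/√0.90 = 1.054.
- Actual two-sided error rate with the factors omitted: 2[1 − Φ(1.96/√(1 − R²))]. At 10%, 1.96 × 1.054 = 2.066, giving 0.039.
- Power with the factors omitted, for an effect that has 80% power when they are included: δ = (1.960 + 0.842)√(1 − R²), and power = Φ[(δ − 1.960)/√(1 − R²)]. At 10%, δ = 2.802 × 0.9487 = 2.658, and (2.658 − 1.960)/0.9487 = 0.736, giving 0.769.

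| Assumed R² | SE ratio | Actual alpha | Power |
|---|---|---|---|
| 0% | 1.000 | 0.050 | 0.800 |
| 1% | 1.005 | 0.049 | 0.797 |
| 2% | 1.010 | 0.048 | 0.794 |
| 5% | 1.026 | 0.044 | 0.785 |
| 10% | 1.054 | 0.039 | 0.769 |
| 20% | 1.118 | 0.028 | 0.729 |

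**4. Simulation check.** 478 subjects, 12 strata, permuted blocks of four, analysis of covariance at one visit, 4,000 runs per value. Block size and stratum shares are assumed, and one visit stands in for the full repeated-measures model. Mean SE ratios were 1.000, 1.010, 1.026, 1.054 and 1.118 at R² = 0, 2, 5, 10 and 20%, which matches the formula. With the factors included, the model SE agreed with the empirical spread of the estimates to within about 1% for R² of 2% to 20%. With them omitted, it was too large by about 3%, 6% and 11% at 5%, 10% and 20%. At R² = 0 the two models behaved alike.

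**5. Cost in degrees of freedom.** (2 − 1) + (2 − 1) + (3 − 1) = 4. One further induction category makes it 5.

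**6. Outputs affected.** The 280-event SAP repeats the interim report's analyses except those it lists. The list of dropped outputs includes the change-from-baseline analysis tables for QLQ-CLL16 (4.0020), QLQ-C30 (4.0070), EQ-5D utility (4.0170) and EQ-5D visual analogue scale (4.0220). These therefore belonged to the interim set. The B-symptoms counterpart, 4.0120, is retained. The final-analysis output list has no PRO questionnaire tables.

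**The case against.** **PRO analyses may not be efficacy analyses under 8.2.** SAP 6.1 assigns the ITT population to efficacy and then separately to PRO analyses, which would be redundant if one included the other. PRO methods have their own Section 13, and the 280-event output list files PRO tables under Health Outcomes. A specific model can also be read as displacing a general rule. This stands far enough to make the breach of 8.2 arguable. The listing of PRO changes under 11.2 weakens it, and it gives no reason to leave the factors out.

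**The PRO model is not the only one without the strata.** A reader might infer that it alone departs from the rule. The Cox model in 11.1 is stepwise at 0.05 with only treatment forced in, so the factors can drop out. The prognostic-marker Cox model in 11.2 does not list them. That objection stands against any claim of a lone exception. The 11.1 model, however, supplements a log-rank test that is itself stratified, whereas the PRO comparison has no stratified test behind it.

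**The harm is small and conservative.** This is correct. Both later analyses are described as descriptive, and PRO p-values are nominal throughout.

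**Changing the model now breaks comparability with the interim report.** This is fair for table 4.0120. Showing both models answers it.

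**Conclusion.** The omission is certain; its effect on precision is conditional. A reader might infer that the PRO intervals are in fact too wide. The documents do not support that, because nothing in them shows that the three factors predict PRO change once baseline score, age group, performance status and Binet stage are fitted. For an assumed R² of 2% to 10%, the standard error is overstated by about 1% to 5.4%, the actual error rate is 0.048 to 0.039, and power that would be 80% is 79% to 77%. There is no bias in the treatment estimate, and no effect at R² = 0.

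A reader might also take this to cover every patient-reported outcome. It covers the scores that are modelled; the Health Change Questionnaire is only tabulated. Section 11.2 also names an area under the curve of change from baseline that Section 13 never specifies, so its adjustment cannot be judged.

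This is a minor, inexpensive improvement and an inconsistency to resolve. It does not threaten the trial's conclusions.

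**What to change.** Add to the 13.1 model, as fixed effects, response at entry, number of previous induction treatments and type of prior treatment. If the additional category for one or more than three inductions is created under 9.2.14, carry it into this model too. Use the eCRF-based strata of 8.2: strata as recorded at randomisation would make the PRO model differ from the other stratified analyses. Sections 13.2 to 13.4 then inherit the change.

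For the 280-event analysis, produce table 4.0120 with the extended model alongside the interim-specified one, so that it stays comparable with the interim report. If the sponsor prefers to keep the model as written, one sentence in 8.2 or 13.1 should exempt the PRO analyses and say why.

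The cost is four or five degrees of freedom against about 478 evaluable subjects, one extra run of a single table, and no new data.
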